8.4.2. Pregnancy report

Subjects who become pregnant at any time will be immediately withdrawn from participation in the study. All appropriate withdrawal assessments may be performed at the discretion of the investigator.

The investigator will collect pregnancy information on any woman subject or partner of a male subject, who becomes pregnant and their partner while participating in this study. The investigator will record pregnancy information on a specific pregnancy notification form and submit it to IntuVigilance Limited (see contact details in section 8.4) within 24 hours after knowledge of a subject's or partner's pregnancy. The subject or partner will also be followed to determine the outcome of the pregnancy, be it full-term or prematurely terminated. Information on the status of the mother and child will be forwarded to ABIVAX or its designee. Follow-up will normally end 6 to 8 weeks following the estimated delivery date but could last up to one year after the delivery.

While pregnancy itself is not considered to be an AE or SAE, any pregnancy complication or elective termination of a pregnancy for medical reasons will be recorded as an SAE. A spontaneous abortion is always considered to be an SAE and will be reported as such.

The time period for collecting pregnancy information is identical to the time period for collecting AEs, as stated in Section 8.5, Time Period, Frequency, and Method of Detecting AEs and SAEs. Pregnancy information is collected from the signing of Pregnancy Follow up Inform Consent or Pregnant Partner Informed Consent to the end of the pregnancy follow-up.

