1.2.4. Preclinical data of ABX464

1.2.4.1. Non-clinical background information

The toxicity of ABX464 and ABX464-N-Glu was studied in a range of rodent and nonrodent species (rats, rabbits, dogs, cynomolgus and marmoset monkeys, and mini-pigs) with treatment durations ranging from 2-weeks to 6/9 months. These studies have demonstrated that ABX464 and ABX464-N-Glu are overall well tolerated. Vomiting and ptyalism were the major clinical sign, and the main target organs of ABX464 toxicity were the gastro-intestinal tract and the liver. The adverse effects noted on these organs were essentially mild/moderate but showed reversibility during the recovery phases.

Plasma exposure to ABX464 and ABX464-N-Glu in humans (based on predicted steady-state exposure in ulcerative colitis patients at the highest proposed dose of 100mg) are calculated as being approximately parity (Cmax) to 4-fold (AUC) for ABX464 and 9-fold (Cmax) to 2-fold (AUC) for ABX464-N-Glu exposure as seen in pivotal chronic toxicology studies.

ABX464 had no significant adverse effects on the nervous and respiratory systems, or on cardiovascular function. ABX464 was shown to be non-genotoxic and ABX464-N-Glu was shown to be non-mutagenic.

Genotoxicity:

ABX464 was found to be non-genotoxic. Its main metabolite, the ABX464-N-Glu was not mutagenic as assessed by an Ames test, an in vitro and an in vivo micronucleus assay.

Reprotoxicity:

Reproductive toxicity was assessed from fertility to postnatal development, in five studies. In rabbits, the maternal NOAEL was considered to be 9mg/kg od and the NOAEL for the embryo-fetal development less than 1mg/kg od. In rats, the maternal NOAEL and the NOAEL for pup development and survival is considered to be lower than 15 mg/kg od. The F1 generation NOAEL is considered to be 40mg/kg od in absence of adverse effect at this dose-level.

Teratogenicity:

ABX464 appears to have teratogenic activity.

Hepatocellular toxicity:

In minipigs the main adverse finding was centrilobular hepatocellular degeneration/necrosis associated with hemorrhage, fibrosis and /or extramedullary hematopoiesis observed at dose levels of 10mg/kg and above. The liver lesions observed in one of the animals administered 5mg/kg od, were not considered adverse. Based on this observation, the NOAEL is 5mg/kg od.

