4.2. Eligibility Criteria

4.2.1. Inclusion Criteria

A subject will be eligible for inclusion in this study only if ALL of the following criteria apply:

- Subjects previously enrolled in the ABX464-101 clinical study who have completed the initial 2-month treatment phase;
- Subjects able and willing to comply with study visits and procedures;
- Subjects with hematological and biochemical laboratory parameters as follows at the D56 visit of the ABX464-101 study:
 - Hemoglobin > 9.0 g dL-1;
 - Absolute neutrophil count $\geq 750 \text{ mm}^{-3}$;
 - Platelets $\geq 100,000 \text{ mm}^{-3}$;
 - Total serum creatinine $\leq 1.3 \times \text{ULN}$ (upper limit of normal);
 - Creatinine clearance $> 50 \text{ mL min}^{-1}$ by the Cockcroft-Gault equation;
 - Total serum bilirubin $< 1.5 \times \text{ULN}$;
 - Alkaline phosphatase, AST (SGOT) and ALT (SGPT) $< 1.5 \times \text{ULN}$;
- Subjects should understand, sign and date the written voluntary informed consent form at the enrolment visit prior to any protocol-specific procedures being performed;
- Females and males receiving the study treatment and their partners must agree to use a highly effective contraceptive method during the study and for 6 months after end of study or early termination. Contraception should be in place at least 3 months prior to study participation. Women must be surgically sterile or if of childbearing potential must use a highly effective contraceptive method. Women of childbearing potential (WOCBP) will enter the study after confirmed menstrual period and a negative pregnancy test. Highly effective methods of contraception include true abstinence, intrauterine device (IUD) or hormonal contraception aiming at inhibition of ovulation, intrauterine hormone releasing system, bilateral tubal ligation, vasectomized partner. True abstinence is defined when this is in line with the preferred and usual lifestyle of the patient. In each case of delayed menstrual period (over one month between menstruations) confirmation of absence of pregnancy is required. This recommendation also applies to WOCBP with an infrequent or irregular menstrual cycle. Female and male patients must not be planning pregnancy during the trial and for 6 months post completion of their participation in the trial. In addition, male participants should use condoms and should not donate sperm as long as contraception is required.

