8.5. Time Period, and Frequency of Detecting AEs, AESIs and SAEs

All AEs, AESIs and SAEs occurring from the time a subject consent to participate in the study until 4 weeks after he or she has completed or discontinued the investigational product must be recorded in the subject's eCRF.

Importantly, SAEs and AESIs will have to be reported, either by email or by Fax, to IntuVigilance Limited within 24 hours of awareness of an SAE/AESI.

Hotline [contact]

Email Address: [contact]

[contact]

Legislative guidance requires also reporting any **related** SAEs to be reported after the subject finished the study if the investigator becomes aware of them.

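### The duty to notify a new pregnancy ends 4 weeks after the last dose, while the protocol requires contraception for 6 months after end of study; the two periods in the protocol should be aligned.

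*Protocol*

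**What the plan says.** Four parts of the protocol bear on this.

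- **Risk.** Section 1.2.4.1 says: "ABX464 appears to have teratogenic activity". It gives a rabbit no-observed-adverse-effect level for embryo-fetal development below 1 mg/kg once daily.
- **Precaution period.** Section 4.2.1 covers female and male subjects as well as partners, all of whom "must agree to use a highly effective contraceptive method during the study and for 6 months after end of study or early termination". Subjects of either sex must also not plan a pregnancy until 6 months after their participation ends.
- **Capture of pregnancies.** Section 8.4.2 has the investigator collect information "on any woman subject or partner of a male subject, who becomes pregnant and their partner while participating in this study". On timing it says: "The time period for collecting pregnancy information is identical to the time period for collecting AEs, as stated in Section 8.5". Section 8.5 runs the AE period "until 4 weeks after he or she has completed or discontinued the investigational product". Section 10.1.3 repeats the restriction to pregnancies arising during participation when it describes the pregnancy consent.
- **Follow-up of a known pregnancy.** The next sentence of 8.4.2 gives a different period, from signature of the pregnancy consent or "Pregnant Partner Informed Consent to the end of the pregnancy follow-up". On duration, the section says: "Follow-up will normally end 6 to 8 weeks following the estimated delivery date but could last up to one year after the delivery".

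The last scheduled pregnancy test is at the End of Study (EoS) visit, 28 days after the last dose (sections 5.1 and 5.2.6). The SAP only lists pregnancy test results (section 11.6.2, Listing 16.2.4.3) and adds no reporting rule.

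**The concern.** The protocol treats conception as something to be prevented for 6 months after end of study, but asks sites to tell the sponsor about new pregnancies only up to 4 weeks after the last dose. These two periods answer to the same named risk and do not match.

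What is at stake is knowledge of exposed pregnancies. If a former subject or a partner conceives in the weeks or months after EoS, the site has no instruction to report it, to seek pregnancy consent, or to follow it to outcome. The sponsor would then lack both the count of such pregnancies and a systematic record of their outcomes. With 22 subjects enrolled (section 1.3), few such pregnancies can be expected, so losing even one matters.

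There is also a drafting problem inside 8.4.2. Two adjacent sentences define the collection period differently. One uses the AE window; the other runs from pregnancy consent to the end of follow-up. A site cannot tell from the text which sentence governs detection and which governs follow-up.

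**Working it through.** The plan states no figure on this point, so there is nothing to reproduce. The check is calendar arithmetic followed by a reading of the reporting routes.

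**Inputs**
- End of the pregnancy/AE window: day 28 after the last dose (8.4.2 through 8.5).
- EoS visit: day 28 after the last dose (5.2.6).
- Contraception: 6 months after end of study or early termination (4.2.1).
- Treatment: 48 months (3.1.1).
- Assumption: 1 month = 365.25/12 = 30.44 days, so 6 months = 182.6 days and 48 months = 1,461 days.

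**1. Post-treatment period, end of study taken as EoS**
Length = 28 + 182.6 = 210.6 days. Without a notification duty = 210.6 - 28 = 182.6 days. Share = 182.6/210.6 = 87%.

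**2. Post-treatment period, 6 months counted from the last dose**
Length = 182.6 days. Without a duty = 182.6 - 28 = 154.6 days. Share = 154.6/182.6 = 85%.

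**3. Sensitivity to the EoS date**
The flow chart allows 4 days either side of day 28. With the AE window fixed at day 28:
- EoS on day 24: (24 + 182.6 - 28)/(24 + 182.6) = 178.6/206.6 = 86%.
- EoS on day 32: (32 + 182.6 - 28)/(32 + 182.6) = 186.6/214.6 = 87%.

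**4. Whole contraception period for a 48-month completer**
- Reading 1: 182.6/(1,461 + 28 + 182.6) = 182.6/1,671.6 = 11%.
- Reading 2: 154.6/(1,461 + 182.6) = 154.6/1,643.6 = 9%.

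**5. Early stoppers**
Under reading 1 the share is 182.6/(T + 28 + 182.6), with T the days on treatment. It is 76% at 1 month, 50% at 5 months, 46% at 6 months and 32% at 12 months. The gap exceeds half of the whole period only for subjects who stop within about 5 months.

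**6. What happens to a pregnancy that begins after day 28**

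| Route | Does it apply? |
|---|---|
| Pregnancy notification (8.4.2) | No: outside the AE window and after participation |
| Scheduled pregnancy test | No: the last is at EoS |
| Follow-up to outcome (8.4.2) | Only once a pregnancy is known and consent is signed |
| Post-study SAE reporting (8.5) | Only if the event is serious, judged related, and reaches the investigator |

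Section 8.4.2 says that pregnancy in itself is neither an AE nor an SAE. An uncomplicated late pregnancy therefore has no route at all, and one whose outcome is judged unrelated has none either.

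**The case against.** **Follow-up is not cut off at 4 weeks.** A reader of the first timing sentence alone might infer that all collection of pregnancy information stops then. The documents do not support that. A pregnancy notified inside the window is followed past delivery, for up to a year. The 4-week limit can bear only on new pregnancies. This stands, and it narrows the point to detection and notification.

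**Late harm is partly covered.** A reader might also infer that nothing that happens after EoS is reportable. That goes too far. Section 8.4.2 makes pregnancy complications, terminations for medical reasons and spontaneous abortion SAEs. Section 8.3 includes congenital anomaly. Section 8.5 requires related SAEs learned of after the study to be reported. This stands as a partial safeguard, but it is passive and depends on a causality judgement. It gives no count of exposed pregnancies.

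**Elimination.** Section 1.2.5 puts the half-life of the metabolite ABX464-N-Glu at about 100 hours. Four weeks is 672 hours, or 6.7 half-lives; under simple exponential decline about 1% would remain (0.5^6.7). That could be offered as a reason for a short reporting window. The protocol does not offer it, and its own precaution period is 6 months. If the sponsor relies on such a reason, it should be written down.

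**Numbers and unseen documents.** The cohort is small, and subjects who enter ABX464-108 continue on drug under rules that are not in these documents. The consent documents were not available either, so subjects may already be told to report later pregnancies. Both limit what can be claimed about practice. Neither removes the mismatch in the protocol text.

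**Conclusion.** The point holds for notification of new pregnancies after treatment. For a subject who stops ABX464 and does not enter ABX464-108, 85-87% of the post-treatment contraception period (155 of 183 days, or 183 of 211) has no duty to notify. The gap opens directly after EoS. These figures rest on 30.44-day months, EoS at day 28, and one of two readings of when the 6 months begin.

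Three further readings are tempting and are not supported:

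- **That most of the at-risk period as a whole is uncovered.** Contraception is also required on treatment, so for a 48-month completer the share is 9-11%.
- **That 8 of the 22 subjects are affected.** Subtracting the 14 treated for more than 3 years (section 1.2.5) from the 22 enrolled gives 8. It does not show who stopped, who could conceive or had a partner who could, or whose 6 months had already elapsed. The documents do not give the number affected.
- **That an absence of pregnancy reports would be presented as reassurance.** No endpoint or summary table concerns pregnancies, so this is conjecture.

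The protocol's statement on teratogenicity is itself qualified, and the point needs nothing stronger. It should be corrected because the two periods serve the same stated risk and the correction is cheap. It affects no efficacy or safety estimate in the SAP.

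**What to change.** - **Section 8.4.2, window:** replace the link to section 8.5 with a notification window for new pregnancies, in female subjects and in partners of male subjects, that ends when the protocol's own contraception requirement ends. Tie it to that requirement rather than to a separate figure, so that the two cannot drift apart.
- **Sections 8.4.2 and 10.1.3, scope:** remove the restriction to pregnancies arising during participation in both places. Changing only 8.4.2 would create a new contradiction with the pregnancy-consent text.
- **Section 8.4.2, two periods:** state separately the period for notifying a new pregnancy and the period for following a notified one, keeping follow-up to outcome as it now stands.
- **EoS visit:** ask subjects to inform the site of any pregnancy in the notification window, with a matching line in the patient information if it is not already there.

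The cost is an amendment of wording and the handling of occasional late notifications. No visit, test or treatment rule changes.

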8.5. Time Period, and Frequency of Detecting AEs, AESIs and SAEs

All AEs, AESIs and SAEs occurring from the time a subject consent to participate in the study until 4 weeks after he or she has completed or discontinued the investigational product must be recorded in the subject's eCRF.

Importantly, SAEs and AESIs will have to be reported, either by email or by Fax, to IntuVigilance Limited within 24 hours of awareness of an SAE/AESI.

Hotline [contact]

Email Address: [contact]

[contact]

Legislative guidance requires also reporting any **related** SAEs to be reported after the subject finished the study if the investigator becomes aware of them.

8.6. Recording AEs and SAEs

Severity of AEs will be assessed according to CTC-AE Classification Version 4.0.

Subjects will be asked to report all AEs as part of the procedures performed at each study visit. The site personnel will document all AEs in the subject's medical record. All AEs subsequently must be recorded in the appropriate eCRF sections.

The following points must be recorded for each event:

- A description of the event in medical terms, not as reported by the subject;
- Date of onset (start date);
- Date of resolution (stop date);
- The time of onset with respect to administering the investigational product;
- The severity of the sign/symptom or clinically significant abnormal laboratory value according to CTC-AE Classification;
- The causal relationship between the investigational product and the occurrence of each AE. This will be assessed by each investigator using clinical judgment. Alternative causes, such as natural history of the underlying diseases, concomitant medications, other risk factors and the temporal relationship of the event to the investigational product will have to be considered. The causality of all AEs should be assessed by the investigator with the following question: Is there a reasonable possibility that the AE may have been caused by the investigational product? And answered "NO" (if not related) and "YES" (if related);
- Action taken regarding the investigational product:
 - No action;
 - Temporary discontinuation;
 - Permanent discontinuation;
- Subject's outcome:
 - Recovered without sequelae / resolved without sequelae;
 - Recovered with sequelae / resolved with sequelae;
 - Recovering/Resolving;
 - On-going;
 - Fatal (for SAEs only).

If in any one subject, the same AE occurs on several occasions, the AE in question must be documented and assessed anew each time.

8.7. Reporting of AESIs and SAEs to ABIVAX or its designee

Throughout the study, the reporting of SAEs and AESIs to the Sponsor or its designee will be done through the SAE and AESI forms.

It is the investigator's responsibility to ensure that the SAE/AESI report is submitted to IntuVigilance Limited **within 24 hours after knowledge of the event(s)**.

The SAE/AESI forms or paper report forms should be completed as thoroughly as possible, with all the available details of the event and signed by the investigator or designee. An assessment of causality should always be provided at the time of the initial report. If the investigator or designee does not have all information regarding the SAE/AESI, he/she should not wait to receive additional information before completing the form and notifying IntuVigilance Limited.

Additional or follow-up information relating to the initial SAE report, will be requested, if necessary. Again, this information is to be completed and submitted through the SAE forms within 24 hours of receipt of the information.

In the rare occasion when the facsimile equipment does not work and in the absence of, the investigator should notify IntuVigilance Limited by telephone within the given timeframe, and send a copy of the SAE report form by email.

8.8. Reporting of SAEs/ to Regulatory Authorities

ABIVAX has a legal responsibility to notify, as appropriate, both the local regulatory authorities and other regulatory agencies about the safety of the investigational product. It is therefore important that the investigator notifies promptly ABIVAX or designee of any SAE, in order for legal obligations and ethical responsibilities towards other subjects to be met.

In addition, the investigator or designee, will comply with the local regulatory requirements (when applicable) in reporting of SAEs to the ethics committee and, if required, to the relevant government authority.

Safety reports on adverse events that are serious AND unexpected AND associated with the investigational product are prepared according to ABIVAX's policy and applicable regulations and are forwarded to the investigators. These reports are filed with the investigator brochure or other appropriate study documentation. It is the Sponsor or its designee and/or investigator's responsibility to notify the IRB or IEC of these reports, if applicable according to local requirements.

9. DATA ANALYSIS AND STATISTICAL CONSIDERATIONS

A summary of the principal features of the statistical analysis of the data will be described here, in the statistical section of the protocol. A more technical and detailed elaboration of the principal features stated in the protocol will be given in the first version of the statistical analysis plan (SAP).

Any amendments to the SAP will be clearly documented and signed prior to the final database lock including justifications and details of their potential impact on the interpretation of the study results.

9.1. Statistical and Analytical Plans

An interim analysis was performed at M12.

The study analysis will be performed following database lock upon the completion of the last subject or upon its early discontinuation whichever occurs first.

9.1.1. Protocol deviations

Protocol deviations will be reviewed and classed as critical (immediate impact on patient safety or data integrity), major or minor during the data-review meeting. Major protocol deviations are defined as deviations liable to bias the evaluation of the main efficacy endpoint. The following deviations will be considered as major (non-exhaustive list):

- Non-compliance with the inclusion or exclusion criteria;
- Non-compliance with the study treatment;
- Intake of prohibited medication;
- Noncompliance with time window.

9.1.2. Definition of study analysis sets

The following datasets will be defined and used for the analyses:

- The **Safety dataset (SAF population)** is defined as those subjects included in the study, who have received at least one dose of the study treatment.
- The **Full Analysis dataset (FAS population)** is defined as those subjects included in the study, who have received at least one dose of the study treatment, and who have at least one baseline data.
- The **Per Protocol dataset (PP population)** is defined as those subjects of the FAS population without any major protocol deviation.

9.1.3. Subjects/Subjects disposition

The number and the percentages of subjects enrolled will be tabulated. The reason for subject exclusions from each of the populations will also be listed. In addition, the number of discontinued subjects with their reason for discontinuation will be tabulated.

9.1.4. Demographic and other baseline characteristics

Demographics and other baseline characteristics will be summarized by treatment arm. This analysis will be conducted on the FAS population.

9.1.5. Treatment compliance

Number of doses will be presented on the FAS population.

9.2. Efficacy Analysis

All efficacy analysis will be conducted on both FAS population and PP population except if otherwise specified.

Descriptive statistics will be presented by treatment arm and include:

- Quantitative variables: mean, standard deviation, minimum and maximum, 95% confidence intervals, median and quartiles will be presented when considered relevant. Number of filled and missing values will also be presented.
- Qualitative variables: count, percentage for each modality and 95% confidence intervals when relevant. Number of missing values will also be presented.

